### Secondary Exploratory Objectives

No multiple comparison adjustment will be performed for analysis of secondary endpoints.

- Assess the association between overall survival and change in each of the following quantitative markers for [F]Fluciclovine and [F]FLT:  $K_1-k_4$ ,  $K_{net}$  and  $K^{trans}$ , from baseline to post therapy. This association will be addressed by Kaplan-Meier curves and associated logrank tests. Cox proportion hazards regression will be used to estimate hazard ratios.
- Assess the association between progression free survival and change in each of the following quantitative markers for [18F]Fluciclovine and [18F]FLT:  $K_1-k_4$ ,  $K_{net}$  and  $K_{trans}$ , from baseline to post therapy. This association will be addressed by Kaplan-Meier curves and associated logrank tests. Cox proportion hazards regression will be used to estimate hazard ratios.
- Assess the ability of [F]FLT and/or [F]Fluciclovine alone or together to predict true progression from pseudoprogression in patients with this clinical dilemma. True progression will be separated from pseudoprogression by subsequent MRI imaging. Receiver operating characteristic curve (ROC) analysis with true progression as outcome and each imaging marker or best combination as predictor will be used for this assessment. Bootstrap methods will be used to assess the standard error.
- A 25% reduction in  $SUV_{max}$  or  $SUV_{mean}$  for each of the PET imaging tracers will be more predictive of longer overall survival, than the current MRI based response criteria. This endpoint will be addressed by informal comparison of Kaplan-Meier curves, log rank p-values, and hazard ratios from separate analyses of overall survival for each imaging parameter.
- A 25% reduction in  $SUV_{max}$  or  $SUV_{mean}$  for each of the PET imaging tracers will be more predictive of time to progression than the current MRI based response criteria. This endpoint will be addressed by informal comparison of Kaplan-Meier curves, log rank p-values, and hazard ratios from separate analyses of time to progression for each imaging parameter.

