## 2.3 Brain Tumor Pseudoprogession

Treatment of high-grade brain tumors (GBM and AA) with chemoradiation (temozolomide/radiation) can cause changes in tumor vascular permeability which alter the pattern of gadolinium enhancement, mimicking tumor progression or recurrence. These temporary vascular permeability changes usually improve or stabilize on follow-up MRI and have been termed “pseudoprogession” (Hoffman et al., 1979, De Wit et al., 2004, Chamberlain et al., 2007, Brandes et al., 2008, Brandsma et al., 2008, Fine et al., 2008, Brandsma and van den Bent, 2009, Chaskis et al., 2009, Wen et al., 2010) to distinguish them from true tumor progression. The lack of a definitive imaging modality to distinguish these post-treatment radiographic imaging changes (PTRIC), including pseudoprogession and radiation necrosis/treatment effect, from true tumor progression presents a major unmet clinical need in the care of GBM patients (Wen et al., 2010). To date, no single imaging modality (including MRI, MRS, and PET) has been able to consistently and accurately distinguish between PTRIC from true tumor progression. At present, only direct examination of tumor histopathology can accurately and consistently discriminate true tumor progression from PTRIC. Furthermore, there is no clear understanding of the molecular, biochemical, and cellular mechanisms mediating PTRIC. This clinical trial will hopefully provide a better understanding of the mechanisms responsible for this clinical dilemma and for the development of a novel PET imaging approach to distinguish PTRIC from true tumor progression.

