A number of quantitative and semi-quantitative imaging biomarkers for each tracer will be computed at each imaging time point, and the change in each biomarker between time-points will also be computed. These data will be compared with changes in tracer uptake before and after therapy and used to determine the semi-quantitative change in [F]FLT and [F]Fluciclovine uptake which is consistent with response based on standard brain tumor response. In addition the imaging biomarkers will be used to determine if they are predictive endpoints (survival, time to progression), and with tumor biologic information (histology, WHO grade, vascularity, MIB-1, VEGF, EGFR, p53, IDH status) in cases when tumor tissue becomes available from standard care. These data will provide pilot information regarding the potential value of concurrent multiple PET biomarkers for predicting tumor behavior prior to the start of therapy, for improved prognostication, for more efficient and effective tumor surveillance, and/or for more appropriate assignment of patients to conventional, aggressive, or investigational therapies early in their clinical courses.

All patients will receive standard tumor-directed therapy and will be monitored with conventional imaging according to standard of care, which may include MRI and FDG-PET as described earlier. The [F]FLT or

[F]Fluciclovine PET research scans will *not* affect clinical decisions. A database of demographic, clinical, and molecular biologic information for each patient will be created. Tissue samples, when available from routine care, will undergo detailed histopathologic evaluations, with results prospectively and systematically recorded. All patients will be followed until the end of the trial (at least 12 months post last imaging assessment) for important clinical endpoints as listed in Table 3.

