## 5.2. Inclusion Criteria

- Two adult patient groups will be eligible for inclusion in this study:
  - Group A: Patients where there is compelling evidence, based on the MRI and/or CT imaging, that a high-grade primary brain tumor is present. Pathologic confirmation will occur with biopsy or surgery.  
Patients whose tumor is felt to be inoperable and a biopsy is performed but no surgery.  
Patients with a newly diagnosed primary malignant brain tumor (WHO Grade III or IV) who will be receiving chemoradiation and who either did not undergo surgical resection or underwent incomplete resection with residual tumor  $\geq 1.0$  cm in greatest diameter by contrast MRI postoperatively.
  - Group B: Patients with pathologically proven malignant brain tumor (WHO Grade III or IV glial-based tumors) who have undergone chemoradiation and have MRI-documented possible recurrence/progression versus treatment effect (pseudoprogression) within 6 months from the time of completion of chemoradiation.
- Patients must be 18 years or older for inclusion in this study. There is little experience with the safety of [F]FLT or [F]Fluciclovine in children, and the risks associated with radiation exposure may be increased for children under 18 years old as well.
- Patients must document their willingness to be followed for up to 24 months after recruitment by signing informed consent documenting their agreement to have clinical endpoints and the results of histopathologic tissue analysis (when tissue becomes available from routine care) entered into a research database.
- All patients, or their legal guardians, must sign a written informed consent and HIPAA authorization in accordance with institutional guidelines.
- Determination of pregnancy status: Female patients who are not postmenopausal or surgically sterile will undergo a serum pregnancy test prior to each set of [F]FLT and [F]Fluciclovine PET scans. A negative test will be necessary for such patients to undergo research PET imaging.

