### 5.6.2. Tissue Collection and Analysis

All patients enrolled on this study will have undergone a neurosurgical procedure (either biopsy or tumor resection) in order to obtain a histological diagnosis of their tumors as part of standard care. Tissue specimens will be analyzed by the attending neuropathologist as part of routine care, who will assign a

histologic diagnosis and tumor grade according to World Health Organization (WHO) criteria. If sufficient tissue is available, specimens are routinely evaluated immunohistochemically for MIB-1, EGFR, p53, and IDH status; and by conventional light microscopy for vascularity. These results are routinely recorded on the surgical pathology report.

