### 6.3. Multi-Tracer Assessments in Conjunction

The exploratory aims of this study will assess the value of multi-tracer imaging endpoints, used in conjunction, over individual PET tracers for tumor characterization, predicting tumor aggressiveness, determination of functional changes that occur in response to therapy, and differentiating between recurrent/progressive tumor and treatment effect/necrosis (pseudoprogression). All three phases of image assessment will be studied: qualitative visual assessment (e.g. image scoring), semi-quantitative measures of tracer uptake (SUVs), and fully-quantitative measures ( $K_1$ - $k_4$ ;  $K_{net}$ ). In each case, combinations of imaging endpoints will be considered in conjunction, such as SUV ratios of tracer pairs, and compared with histologic measurements and clinical outcomes.

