## 7. DATA ANALYSIS AND STATISTICS

### 7.1. Validation of Multi-Tracer PET Imaging Technology

This study will explore several hypotheses and provide preliminary exploratory data in the value of the two PET tracers [F]FLT and [F]Fluciclovine alone and in conjunction to assess response and differentiate tumor recurrence/progression from treatment effect/necrosis (pseudoprogression). The broader question of validating precisely what physiological quantity or process that each tracer/imaging endpoint measures and how these correlate with clinical endpoints and histologic data, when available, is the purpose of the study.

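### The pseudoprogression ROC takes its label from later MRI only, with no provision for patients who have histology of the suspect lesion

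*Combined protocol and SAP*

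**What the plan says.** Section 7.2 (Secondary Exploratory Objectives) plans a ROC analysis with true progression as the outcome, each imaging marker or the best combination as predictor, and a bootstrap standard error. The outcome is defined in one sentence: "True progression will be separated from pseudoprogression by subsequent MRI imaging". No other source is named, and there is no order of precedence and no rule for a lesion that later MRI cannot classify.

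Section 2.3 bears on that choice in two ways. It supports serial MRI, because the "temporary vascular permeability changes usually improve or stabilize on follow-up MRI". It also says that, at present, "only direct examination of tumor histopathology can accurately and consistently discriminate true tumor progression from PTRIC", where PTRIC means post-treatment radiographic imaging changes.

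On tissue, section 4.3 states: "Tissue samples, when available from routine care, will undergo detailed histopathologic evaluations, with results prospectively and systematically recorded". Under section 5.2, patients agree to have the "results of histopathologic tissue analysis (when tissue becomes available from routine care) entered into a research database" during follow-up of up to 24 months. Section 5.6.2 concerns the procedure done "in order to obtain a histological diagnosis of their tumors as part of standard care", which is the diagnostic specimen.

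**The concern.** The protocol names histopathology as the accurate discriminator and provides for recording it, yet the rule that creates the ROC outcome does not use it. A patient with routine-care histology of the suspect lesion would still be labelled by MRI. If that lesion had been resected, later MRI might be unable to classify it, and section 7.2 does not say what happens then.

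Wrong labels bias the AUC, and resampling patients with the same labels does not reveal that bias. Its direction is not fixed. Errors unrelated to PET pull the AUC towards 0.5. Errors that PET shares can push it up. Shared error is plausible for FLT SUV, because section 2.4.1 describes that image as dominated by transport across the blood-brain barrier. The argument is not extended to Fluciclovine, whose uptake section 2.4.2 reports as not depending on barrier integrity.

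Leaving the rule unstated also means that any decision to let histology override MRI could be taken after the PET results are known.

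**Working it through.** **Text check.** The question is whether any other section gives histology a role in the label.

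- Section 6.3: combined imaging endpoints are to be "compared with histologic measurements and clinical outcomes". This is a comparison, not a labelling rule.
- Section 7.1: for each imaging endpoint, "how these correlate with clinical endpoints and histologic data, when available, is the purpose of the study". This is a general aim, not a labelling rule.
- Section 5.6.2: diagnostic tissue, which cannot label a lesion that appears after chemoradiation.
- Appendix B: no tissue item at imaging session 3.

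Section 7.2 therefore stands as the only rule. Sections 6.3 and 7.1 are context and do not contradict it.

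**Size.** The plan gives no figure to reproduce here: no MRI error rate, no tissue rate and no number of patients in the ROC. The following are assumptions: true AUC 0.85; half the patients with true progression; MRI label error e = 10% or 20%; suspect-lesion tissue in a random fraction h = 10% or 30%; histology correct. The 30 patients come from section 5.1. Using all of them is an upper bound, since not every patient will reach the third imaging time point.

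*Patients with tissue:* 30 × 0.1 = 3 to 30 × 0.3 = 9.

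*Labels corrected:* 30 × h × e, from 30 × 0.1 × 0.1 = 0.3 to 30 × 0.3 × 0.2 = 1.8.

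*Errors independent of PET.* With equal classes and symmetric error, observed AUC = 0.5 + (0.85 − 0.5) × (1 − 2e′), where e′ = e(1 − h) is the error left after relabelling.

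- e = 10%, h = 0: 0.5 + 0.35 × 0.80 = 0.780
- e = 10%, h = 30%: e′ = 0.07, so 0.5 + 0.35 × 0.86 = 0.801
- e = 20%, h = 0: 0.5 + 0.35 × 0.60 = 0.710
- e = 20%, h = 30%: e′ = 0.14, so 0.5 + 0.35 × 0.72 = 0.752

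*Errors shared with PET.* This was simulated with a binormal model (2,000,000 subjects). The PET marker and a latent MRI score are correlated within each true state, and the MRI score is cut at its midpoint to give error e.

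| e | Correlation | AUC, h = 0 | AUC, h = 10% | AUC, h = 30% |
|---|---|---|---|---|
| 10% | 0 | 0.780 | 0.787 | 0.801 |
| 10% | 0.4 | 0.846 | 0.847 | 0.847 |
| 10% | 0.6 | 0.883 | 0.880 | 0.873 |
| 10% | 0.8 | 0.921 | 0.914 | 0.899 |
| 20% | 0 | 0.710 | 0.724 | 0.752 |
| 20% | 0.4 | 0.815 | 0.819 | 0.826 |
| 20% | 0.6 | 0.872 | 0.870 | 0.865 |
| 20% | 0.8 | 0.933 | 0.924 | 0.908 |

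The rows at correlation 0 match the formula. The change from using tissue is +0.007 to +0.042 at correlation 0, 0.000 to +0.010 at 0.4, −0.002 to −0.010 at 0.6, and −0.007 to −0.025 at 0.8. In nearly all cases the AUC moves towards 0.85.

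*Sensitivity to assumptions.* With 5% histology error the change is +0.004 to +0.031 at correlation 0 and −0.011 to −0.035 at 0.8. With true AUC 0.75 and error-free histology it runs from −0.045 to +0.030.

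*Sampling error.* The Hanley–McNeil variance is [A(1 − A) + (n₁ − 1)(q₁ − A²) + (n₂ − 1)(q₂ − A²)]/(n₁n₂), with q₁ = A/(2 − A) and q₂ = 2A²/(1 + A). At A = 0.85, q₁ = 0.7391, q₂ = 0.7811 and A² = 0.7225.

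- 15 v 15: [0.1275 + 14 × 0.0166 + 14 × 0.0586]/225 gives SE 0.072
- 8 v 8 (assumed): [0.1275 + 7 × 0.0166 + 7 × 0.0586]/64 gives SE 0.101

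Every shift above is smaller than either standard error.

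**The case against.** The strongest reply is that follow-up MRI is close to how the protocol describes pseudoprogression in the first place, and that the histopathology sentence in section 2.3 concerns a wider class that includes radiation necrosis. That supports MRI as the default, which is not disputed. It does not say what should decide when tissue of the suspect lesion is in hand.

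A second reply is that the tissue provisions mean only the diagnostic specimen. Section 5.6.2 does, but the agreement in section 5.2 is broader. It applies to every patient, including Group B, whose pathology is already proven at entry, and it covers tissue that becomes available over up to 24 months. It remains true that nothing plans tissue at suspected progression, so possibly no patient will have it.

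A third reply is that the gain depends on good histology. This stands in part. If 20% of treatment-effect specimens were read as progression (also an assumption), then at e = 10% the gain with independent errors disappears, and at correlation 0.4 the AUC moves away from the truth, from 0.847 to about 0.84 to 0.83. At e = 20% with independent errors a gain remains, from 0.710 to about 0.72 to 0.73. Mixed specimens therefore need a rule fixed in advance.

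Finally, the shared-error correlations are illustrative, since the documents support no particular value. The Fluciclovine statement in section 2.4.2 also rests on a study that the reference list describes as one of low-grade glioma in rats. The shift is below sampling error either way.

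**Conclusion.** The concern holds, at minor severity. Section 7.2 labels by subsequent MRI only, and no other section brings histology into the label. Where suspect-lesion histology exists, the rule as written sets aside what the protocol itself calls the accurate source. The case for change rests on fixing the outcome definition before PET results are known, and not on a large numerical gain. The size estimates depend wholly on assumed error rates, tissue rates, prevalence, true AUC and error correlation. If no patient has such tissue, the result is unchanged. The primary overall survival analysis is not affected.

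**What to change.** Add to section 7.2:

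- Where routine-care histopathology of the suspect lesion, obtained at or after suspected progression, exists, it decides the label. Otherwise subsequent MRI decides.
- How a specimen containing both tumor and treatment effect is labelled, stated in advance.
- Labels are assigned without knowledge of the PET results.
- The number of labels from each source is reported.
- The AUC with MRI-only labels is reported as a sensitivity analysis, in patients whom MRI can classify.

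The cost is a few sentences. No biopsy or scan is added, and the results used are those the protocol already provides for recording when available. The drawback is a reference standard with two sources, one of them drawn from patients selected for surgery. The source counts and the sensitivity analysis make that visible but do not remove it.

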The data from multiple PET biomarkers combined with histologic and clinical data will enable identification and development of PET biomarker profiles which correlate with (and might be predictive of) tumor aggressiveness and clinical outcomes. The three imaging time point assessments serve multiple uses in this initial exploratory study. If baseline imaging can predict tumor aggressiveness and clinical outcomes, such imaging may potentially be used to guide selection of conventional, aggressive, or investigational therapies. The second time point, within 1-4 weeks after 6wks of chemoradiotherapy, will provide a measurement of tumor response that may potentially differentiate tumors that will progress rapidly from those that will not (changes in imaging biomarkers between exams 1 and 2 will likely be important for this determination). Finally, the multi-tracer array at the time of treatment effect (pseudoprogression) versus true recurrence/progression may yield new insights into the physiology and biology of these tumors, and multi-tracer imaging may help to differentiate recurrence from radiation necrosis/treatment effect (pseudoprogression). We believe the complementary value of the two tracers in conjunction has much greater potential for meeting these goals than any one tracer alone. For example, tumors with high proliferation ([F]FLT) and/or growth ([F]Fluciclovine) may respond best to anti-EGFR-directed agents or conventional cytotoxic chemotherapies. Of specific interest, is there a multi-tracer PET signature that distinguishes between treatment effect (pseudoprogression) and true progression/recurrence that will have important clinical utility? These questions will be studied in detail, developing formal hypotheses that will be tested in future phase II/III clinical trials.

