### 6.1.3. [F]FLT Fully-Quantitative Assessment

Quantitative assessment of [F]FLT uptake will be performed by mathematical modeling of time activity curves for [F]FLT and its metabolites in blood and tissues. Several methods of analysis are being considered for evaluating [F]FLT images and results. A plausible scheme is outlined in the figure below.

The compartments describe the kinetic behavior of [F]FLT. Its transport across cell membranes is governed by two rate constants,  $K_1$  and  $k_2$ . The phosphorylation of [F]FLT is governed by the rate constant  $k_3$ . Evidence from FLT experiments in dogs suggests that [F]FLT is retained in cells without significant dephosphorylation ( $k_4$ ). We will initially assume that  $k_4$  is zero to simplify the modeling equations; the Akaike Information Criterion (AIC) will be used to determine if the time-activity curves support the more complex model ( $k_4 \neq 0$ ), which will then be used as indicated.

We will investigate the contribution of the labeled metabolite. If the labeled metabolite is restricted to the plasma space and urine and if the rate constant  $k_4$  is negligible, then the [F]FLT flux constant,  $K_{FLT}$  (mL/min/g), will be computed using graphical analysis (Patlak et al., 1983, Patlak and Blasberg, 1985). In the event that the [F]FLT metabolite contribution in tissue is significant, we will investigate the use of a metabolite-corrected flux constant as a measure of [F]FLT uptake (Mankoff et al., 1997, Muzi et al., 2005a, Muzi et al., 2005b, Shields et al., 2005, Muzi et al., 2006).

The parameters of interest for this model are those directly linked to DNA synthesis—specifically,  $k_3$  and  $K_{flux}$ , as they represent the phosphorylation of [F]FLT to reflect cellular proliferation. We will correlate these rates with proliferative (MIB-1) indices on histological tissue and S phase fraction determined by flow cytometry when these are available.

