### 6.2.3. [F]Fluciclovine Fully-Quantitative Assessment

Fully-quantitative compartment modeling analysis of the dynamic [F]Fluciclovine-PET images will be performed according to the two-compartment model shown below, which has been previously described (Sasajima et al., 2013, Sørensen et al., 2013). As with the other tracers, parameters of interest include individual rate parameters ( $K_1$ ,  $k_2$ - $k_4$ ) and the net uptake parameters. The primary imaging endpoints for [F]Fluciclovine are not yet fully understood, and will in part be elucidated by this study. Of interest, the second-order retention ( $k_3$ ) and reversible ( $k_4$ ) parameters for this tracer have high potential for differentiating inflammatory processes occurring after radiotherapy from residual tumor activity.

Compartment modeling techniques will be applied to the dynamic PET data to obtain estimates of kinetic rate parameters ( $K_1$ ,  $k_2$ - $k_4$ ) and FDG net uptake ( $K_{net}$ ). Individual rate parameters will be computed using full compartment-modeling techniques according to the two-tissue compartment model shown below. Commercially available PET analysis software (e.g. PMOD Technologies LTD., Zurich, Switzerland) will be used. The net uptake parameter will be computed from both full compartment modeling and Patlak graphical analysis (Patlak et al., 1983, Patlak and Blasberg, 1985), both of which are standard and accepted methods.

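### The pseudoprogression ROC scores a best combination chosen in the same patients and bootstraps only its standard error, so the reported AUC will be too high

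*Combined protocol and SAP*

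**What the plan says.** Section 7.2 (Secondary Exploratory Objectives) addresses whether either tracer, or both jointly, can tell true progression from pseudoprogression. It plans an ROC analysis "with true progression as outcome and each imaging marker or best combination as predictor will be used for this assessment". The outcome is set by later imaging: "True progression will be separated from pseudoprogression by subsequent MRI imaging". Resampling has one stated purpose: "Bootstrap methods will be used to assess the standard error". The section also states: "No multiple comparison adjustment will be performed for analysis of secondary endpoints".

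No combination is named. Section 6.3 admits visual scores, SUVs and kinetic parameters, and adds that "combinations of imaging endpoints will be considered in conjunction, such as SUV ratios of tracer pairs". Section 6.1.2 adds tumor-to-white-matter and tumor-to-cortex ratios. Table 3 in section 4.3.1 lists four uptake measures per tracer, but as contents of a database and not as the predictors for this ROC. On kinetic analysis, section 6.1.3 leaves the FLT method open ("Several methods of analysis are being considered for evaluating"), and section 6.2.3 says the primary fluciclovine imaging endpoints "are not yet fully understood, and will in part be elucidated by this study".

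The document has no rule for what counts as best, no weights, no hold-out set, no cross-validation and no optimism correction. The text after Table 3 describes the aim as "developing formal hypotheses that will be tested in future phase II/III clinical trials".

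**The concern.** If the combination is not fixed in advance, calling it best means searching candidates against the outcome and keeping the winner. Scoring the winner in the patients who chose it gives an apparent AUC that is biased upward in two ways: selection (the highest of many noisy AUCs is kept) and fitting (the weights are tuned to these patients). The bias is worst with few patients and many candidates, which is the situation here.

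A bootstrap used only for the standard error resamples the chosen score and reports its variability. The centre stays at the inflated value, so an interval built on it is centred too high.

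This analysis is the plan's answer on the value of the two tracers for pseudoprogression, and section 4.3.1 singles out a multi-tracer signature for this purpose as being of particular interest. An inflated AUC could carry an uninformative combination forward into the design of a later trial.

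**Working it through.** **1. The plan's own figure.** There is none to reproduce. The plan gives no AUC, sample size or precision for the ROC. The total of 30 patients (section 5.1) is an upper bound. The N = 22 in section 7.3 counts patients with post-chemoradiation scans for the survival endpoint. The number at the pseudoprogression time point is therefore assumed: n = 10, 20 or 30, half with true progression.

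**2. Number of candidates.** Table 3 gives 4 per tracer, so 2 × 4 = 8. SUVmax, SUVmean, K1, k2, k3, k4 and Knet give 7 per tracer, so 2 × 7 = 14 before visual scores and ratios. The main simulation uses 2 or 4 markers per tracer (4 or 8 in total), hence 2 × 2 = 4 or 4 × 4 = 16 cross-tracer pairs.

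**3. Method.** All markers are normal noise, so the true AUC is 0.50. Within-tracer correlation ρ is 0 or 0.8, and the tracers are independent.

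- AUC = P(score in progression > score in pseudoprogression), ties counted as half.
- Chosen pair: the highest in-sample AUC among two-marker linear discriminants.
- Interval: apparent AUC ± 1.96 × bootstrap SE, with the chosen score held fixed.
- Optimism: mean over resamples of (AUC in the resample − AUC of that same rule in the original sample), with selection and fitting redone each time.
- Corrected AUC = apparent AUC − optimism.

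Each setting has 1,000 data sets with 100 stratified resamples (Monte Carlo SE of the mean apparent AUC 0.002-0.003).

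**4. Mean AUC with no signal, apparent → corrected.**

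| Markers, ρ | n=10 | n=20 | n=30 |
|---|---|---|---|
| 4, 0.8 | 0.813 → 0.637 | 0.709 → 0.568 | 0.667 → 0.549 |
| 4, 0 | 0.835 → 0.649 | 0.726 → 0.574 | 0.686 → 0.559 |
| 8, 0.8 | 0.862 → 0.668 | 0.749 → 0.585 | 0.699 → 0.561 |
| 8, 0 | 0.917 → 0.724 | 0.790 → 0.613 | 0.732 → 0.577 |

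Inflation runs from 0.667 − 0.50 = 0.167 to 0.917 − 0.50 = 0.417. After correction, 0.549 − 0.50 = 0.049 to 0.724 − 0.50 = 0.224 remains.

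**5. How often noise looks convincing (range over the four settings).**

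| | n=10 | n=20 | n=30 |
|---|---|---|---|
| Fixed-score interval lies above 0.50 | 52-91% | 38-78% | 33-73% |
| Apparent AUC ≥ 0.80 | 60-95% | 15-46% | 3-12% |
| Corrected AUC ≥ 0.80 | 19-32% | 4-5% | 1% |

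**6. Wider search.** A separately coded simulation (400 runs per setting, correlation 0 or 0.5) lets the best predictor be any single marker in either direction or any fitted two-marker pair. With 4 / 8 / 14 candidates and no signal, the mean apparent AUC is about 0.85 / 0.93 / 0.98 at n=10, 0.74 / 0.80 / 0.85 at n=20 and 0.69 / 0.75 / 0.79 at n=30. One fixed marker, scored without selection, averages about 0.50. One pre-specified pair with weights fitted in the same patients still averages 0.73 at n=10 and 0.63 at n=30.

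**7. With a real signal.** One of four markers has true AUC 0.70 (correlation 0.5; 60 simulated trials with 60 resamples each, so less precise). At n=15 the apparent AUC is 0.82, the corrected AUC 0.68 and the true AUC of the selected rule 0.64. At n=30 they are 0.79, 0.70 and 0.68.

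**8. Mildest rule.** With equal weights and direction fixed in advance, selecting only which pair to report gives 0.58-0.79, 0.55-0.70 and 0.54-0.66 at n = 10, 20 and 30.

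**The case against.** The strongest reply has four parts.

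*The plan does not say that the combination is data-chosen, and does not name the AUC, an interval or a test.* This is correct as to wording. But with no combination named, best has no meaning other than best in the data, and the AUC is the natural ROC summary that carries a standard error. The interval in step 5 is an added illustration, not a planned analysis.

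*The marker set is less open than it looks.* Table 3 lists four measures per tracer, and the remarks on methods in 6.1.3 and 6.2.3 concern kinetic modelling, so they bear only indirectly on ROC predictors. This stands in part. But Table 3 is not tied to this analysis, 6.3 and 6.1.2 go beyond it, and its 8 markers are already the upper setting in step 4.

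*Most of the inflation comes from picking any winner, not from combining tracers.* This largely stands. With direction left free, the best single noise marker reaches 0.75-0.84, 0.68-0.74 and 0.64-0.69 at n = 10, 20 and 30, so the fitted pair leads by only about 0.02-0.08. Under equal weights with fixed direction the pair can trail: at n=10 the low end is 0.58, against 0.67 for the best single marker. So the plan need not always favour the combination over single markers. The winner's AUC is inflated either way.

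*The work is exploratory, single-marker results are planned too, scans do not affect care, and formal testing is left to later trials.* All true, and this limits the harm. It does not correct the number that this trial would report.

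**Conclusion.** The concern holds. As written, section 7.2 would report an AUC for a selected combination with its selection and fitting optimism left in, and the planned bootstrap does not address it.

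The direction is the same in every setting examined. The size depends on quantities the plan does not give: patients in the analysis, number and correlation of candidates, case mix and combination rule. For uninformative tracers the average inflation is about 0.17 to 0.42 with a fitted pair. It is 0.54 − 0.50 = 0.04 in the mildest case (n=30, equal weights, fixed direction). Even with all 30 patients and only 4 markers, a fitted pair averages 0.67-0.69. These are average biases, not predictions for one data set. A full listing of every single-marker AUC is not biased in this way unless the highest one is singled out.

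Because the objective is secondary and exploratory, this should be corrected in the plan but does not touch the primary survival endpoint.

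**What to change.** In section 7.2:

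1. Before imaging data are linked to the progression outcome, list the candidate markers for each tracer and the combination rule. Name one primary combination with its weights and direction fixed, for example an equally weighted sum of one standardized marker per tracer. Its AUC then carries no selection or fitting optimism. Fixing the pair but fitting the weights is not enough (step 6).
2. For any combination chosen from the data, repeat the whole selection and fitting inside every bootstrap resample, subtract the mean optimism, and report the corrected AUC with its interval beside the apparent AUC. Treat a best single marker in the same way if it is highlighted.
3. State the number of patients and of progression events in the analysis, and say that some optimism remains after correction, most of all near n=10. The plan already calls the objective exploratory, so no new label is needed.

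The cost is a few SAP lines and modest programming on a bootstrap that is already planned, with no added patients or scans. Reported AUCs will be lower. A fixed list may leave out a marker that later looks useful, but that marker can still be reported as unplanned.
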